9.5. Derived and Transformed Data

9.5.1. Baseline

The protocol specifies Day 0 as Baseline/Treatment Start date, but the CDISC standard is to refer to the Baseline/Treatment Start date as Day 1; therefore Baseline/Treatment Start date will be referenced as Day 1 in this document. A table indicating the target study day for each planned visit is in Section 9.5.3.

The baseline value of a variable is defined as the last available value measured prior to dosing on or before the date of first dose (Day 1), unless otherwise specified.

If the last available value occurs on Day 1 but the time of the assessment is not collected, then the assessment will be assumed to be prior to dosing. Noted exceptions to this rule are concomitant medications and AEs; these will be considered as being concomitant and treatment-emergent, respectively, if the start date occurs on the first day of dosing.

However, if time is available for an AE or concomitant medication and the end time is earlier than the start time of first dose of IP, the AE or concomitant medication will not be considered as treatment-emergent or concomitant, respectively.

9.5.2. Study Day

Study Day is the number of days from the treatment start date to a study date of interest (e.g. event start date) and is calculated as follows:

If condition is...	Then Study Day is...
study date < treatment start date	study date – treatment start date
study date is ≥ treatment start date	study date – treatment start date + 1

Note: Study Day cannot be zero. If either date is missing, then Study Day is missing.

9.5.3. Analysis Visit and Analysis Visit Number

Where applicable, the data are summarized per the planned visit assignment in the data. The visit windows below will be used to assign events to scheduled visits for tabular summaries of time to withdrawal from study, time to premature withdrawal from IP by clinical visit, cumulative time to mortality (On-Treatment Period) and cumulative time to mortality (On-Study Period).

Analysis Visit	Analysis Visit Number	Target Study Day ¹	Interval Start Day	Interval End Day
Screening	10	-30	Na	Na
Treatment Period visits:				
Baseline	25	1	Na	Na
Week 2	30	15	1	15
Week 4	40	29	16	29
Week 8	50	57	30	57
Week 12	60	85	58	85
Week 16	70	113	86	113
Week 20	80	141	114	141
Week 24	90	169	142	169
Week 28	100	197	170	197
Week 32	110	225	198	225
Week 36	120	253	226	253
Week 40	130	281	254	281
Week 44	140	309	282	309
Week 48	150	337	310	337
Week 52	160	365	338	[2]

¹Study Day with Baseline/Treatment Start Date as Day 1.

[2] Any events on or after Day 338 will be assigned to Week 52

9.5.4. Subject Years of Follow-Up to Week 52

Start and end dates for study periods are defined in Section 9.1. For calculation of exposure adjusted incidence rates (during the on-treatment period) and study follow-up adjusted incidence rates (during the on-study period), the following will be derived (in years) for each subject. Additionally, for summaries of subject follow-up time, the off-treatment, missing and total possible follow-up will be derived in years.

Note: The On-Study (to Week 52) terminology reflects the intended duration of follow-up for mortality and AESIs during the main study (i.e. 52 weeks). Some subjects will have less than 52 weeks of follow-up (e.g. where the subject has died or withdrawn from the study). The terminology ‘follow-up’ has been used to describe the time periods during which subjects are followed up for event assessment during the main 1-year study and does not refer to the post-treatment follow-up period in Years 2-5 (described in Section 9.1.2).

On-Treatment Follow-Up: Mortality and Malignancy and Other Data

$[(\text{End Date for On-Treatment Period} - \text{Study Treatment Start Date}) + 1]/365.25$

On-Study Follow-Up (to Week 52): Mortality and Malignancy

$[(\text{End Date of On-Study Period for Assessment of Mortality and Malignancy (to Week 52)} - \text{Study Treatment Start Date}) + 1]/365.25$

On-Study Follow-Up (to Week 52): Other Data

$[(\text{End Date of Study Period for assessment of all data excluding mortality and malignancy (to Week 52)} - \text{Study Treatment Start Date}) + 1]/365.25$

Off-Treatment Follow-Up Time: Mortality and Malignancy

$[(\text{End Date for On-Study Period for Assessment of Mortality and Malignancy} - [\text{End Date for On-Treatment Period} + 1]) + 1]/365.25$

Off-Treatment Follow-Up Time: Other Data

$[(\text{End Date for On-Study Period for assessment of all data excluding mortality and malignancy} - [\text{End Date for On-Treatment Period} + 1]) + 1]/365.25$

Total Possible Follow-Up Time: Mortality and Malignancy

$[(\text{Possible Follow-Up Date} - \text{Study Treatment Start Date}) + 1]/365.25$

For subjects whose end of on-study period for mortality and malignancy is on or after Study Day 358 (lower allowable visit window for Week 52 assessment) the possible follow-up date will be assigned as the end date for the on-study period for assessment of mortality and malignancy.

For subjects whose end of on-study period for mortality and malignancy is before Study Day 358 (lower allowable visit window for Week 52 assessment) the possible follow-up date will be assigned as the minimum of Study Day 365 and date of death.

Total Possible Follow-Up Time: Other Data

$[(\text{Possible Follow-Up Date} - \text{Study Treatment Start Date}) + 1]/365.25$

For subjects whose end of on-study period for all data excluding mortality and malignancy is on or after Study Day 358 (lower allowable visit window for Week 52 assessment) the possible follow-up date will be assigned as the end date for the on-study period for assessment of all data excluding mortality and malignancy.

For subjects whose end of on-study period for all data excluding mortality and malignancy is before Study Day 358 (lower allowable visit window for Week 52 assessment) the possible follow-up date will be assigned as the minimum of Study Day 365 and date of death.

Missing Follow-Up Time (Years): Mortality and Malignancy / Other Data

Total possible follow-up time – (on-treatment follow-up + off-treatment follow-up)

9.5.5. Change from Baseline

Change from baseline will be calculated as:

$$\text{Visit value} - \text{baseline value.}$$

If either value is missing the change from baseline will be missing.

9.5.6. Percent Change from Baseline

Percent change from baseline will be calculated as

$$\frac{\text{Visit Value} - \text{Baseline Value}}{\text{Baseline Value}} \times 100.$$

If the baseline value is zero or missing, then the percent change should be set to missing.

9.5.7. Treatment Completer

A “treatment completer” is defined as a subject who does not discontinue study agent prematurely. Treatment completion date or treatment discontinuation date is defined using the date from SDTM.DS where DSSCAT='STUDY TREATMENT'. Treatment completion date is assigned for subjects who completed study treatment (DSDECOD='COMPLETED') and study treatment discontinuation date is assigned for subjects who did not complete study treatment (DSDECOD not missing and not equal 'COMPLETED').

9.5.8. Study Completer

A “study completer” is defined as a subject who does not withdraw from the study prior to Week 52. Data for ‘study completers’ can include off-treatment data for subjects who discontinue study agent but continue on the visit calendar for study assessments.

Note: Each subject should have a date of study withdrawal or completion. Study withdrawal or completion date is defined using the date from SDTM.DS where DSSCAT='STUDY CONCLUSION'. Study completion date is assigned for subjects who completed the study (DSDECOD='COMPLETED') and study discontinuation date is assigned for subjects who did not complete the study (DSDECOD not missing and not equal 'COMPLETED').

9.5.9. Analysis Age

Analysis age is derived in years relative to the treatment start date for randomized subjects, and is calculated in SAS as follows:

INTCK ('YEAR', Date of birth, Date of treatment start date, 'C').

For subjects who are randomized but do not receive study agent and therefore have no treatment start date, randomization date will be used instead.

9.5.10. Race Hierarchical Rule

If multiple race categories are checked on the eCRF, the subject will be assigned to a unique race group based on which of the races checked appears first in the list below:

- Native Hawaiian or Other Pacific Islander
- American Indian or Alaska Native
- Asian
- Black or African American
- White

For example, if Black or African American and Asian are both checked, then the subject will be assigned as Asian since it appears highest in the list. In the race and racial combination details table, subjects with multiple race categories checked will be reported in the race per the hierarchical rule as well as in the multiracial category. Subjects who select more than one Asian category and no other non-Asian categories will be represented in the Mixed Asian Race category as well as the Asian category. Similarly, subjects who select both white categories and no non-white categories will be represented in the Mixed White Race category as well as the White/Caucasian category. The Mixed Asian Race and Mixed White Race categories will only appear in the table if a subject selects multiple Asian or multiple white categories, respectively.

For the Race subgroup, if a subject selects multiple races they will be assigned “Black” if any of the races is “Black or African American”, i.e., the hierarchical rule will not apply in this instance (see Section 8.3).

9.5.11. SLE Disease Duration

SLE Disease Duration is defined as

$$\frac{\text{Treatment Start date} - \text{SLE diagnosis date} + 1}{365.25}$$

If either date is missing, then SLE Disease Duration will be missing. Partial dates for SLE diagnosis date will be imputed as described in Section 9.4.3.

9.5.12. Mortality and Protocol-Defined AESI

Mortality status will be derived from the SAE data, where outcome is fatal.

The derivation for the protocol-defined AESIs are provided in the table below. Treatment emergent AESIs (see Section 9.5.13 and Section 9.5.15) only will be summarized.

Where the protocol defined AESI utilize definitions from the PSAP, the detailed derivations from the PSAP are provided in [Appendix 6: PSAP Sections for AESI Reporting](#). AESI are identified per the preferred terms and other criteria described in the PSAP.

Protocol-Defined AESI (see Section 2.2.1 and Section 2.2.3 for clarification)	Definition	Programming Derivation (Protocol Definition)
Serious infections	SAEs within Infections and Infestations SOC.	SOC=Infections and Infestations & AESER = 'Y'
Opportunistic infections and other infections of interest	"All Infections" per PSAP definition to cover all OI and infections of interest.	CQ06NAM ne " or CQ07NAM ne " or CQ08NAM ne "
Non-melanoma skin cancers (NMSC)	NMSC per PSAP definition.	CQ00MLFL = 'Y' and CQ03NAM ne " and CQ03NMFL = 'Y'
Malignancies (excluding NMSC)	PSAP defined, "all malignancies excluding NMSC".	[CQ00MLFL = 'Y' and (CQ01NAM ne " or CQ02NAM ne " or (CQ03NAM ne " and CQ03NMFL ne 'Y'))] Or (CQ04NAM ne " and CQ04NPFL = 'Y')
Psychiatric events suggesting serious mood disorders and anxiety	Serious events from the depression CMQ (PSAP defined – depression including mood disorders and anxiety).	CQ09NAM ne " and AESER = "Y"
Suicidality (C-SSRS)	Any treatment-emergent C-SSRS suicidal ideation (1-5) or suicidal behavior (6-10) (defined in Section 9.5.15) – i.e. maximum ideation score worsens relative to pre-treatment or maximum behavior score worsens relative to pre-treatment	C-SSRS Ideation categories 1-5 and Behavior categories 6-10; any subject with ideation or behavior that is treatment-emergent (defined in Section 9.5.15).
Serious infusion and hypersensitivity reactions	Serious infusion and hypersensitivity reactions per the PSAP definition. Includes all SAEs from the anaphylactic reactions CMQ broad search (see Section 11.2.4, includes events on the day of the infusion or within 3 days after the infusion).	CQ05NAM ne " and AESER='Y' and AEINF3FL='Y'

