1.4 Benefit-Risk Assessment

1.4.1 Risk Assessment

Belimumab administered by IV infusion is indicated for reducing disease activity in adult patients with active autoantibody positive SLE who are receiving standard therapy. The benefit/risk profile of belimumab for SLE remains favorable.

Identified risks include hypersensitivity/infusion reactions and infections. Potential risks (i.e., based on pharmacology but no association identified to date) include progressive multifocal leukoencephalopathy (PML); malignancies; immunogenicity; effects on immunizations (including interactions with live vaccine); and psychiatric events including depression and suicidality.

The most common AEs reported in the primary safety population of adults with SLE were associated with hypersensitivity/infusion related reactions, infections, and symptoms consistent with SLE. The majority of reports of infusion-related and hypersensitivity reactions were non-serious and include symptoms such as nausea, vomiting, diarrhea, chills, fever, rash, urticaria, pruritus, headache, dizziness, and dyspnoea. However, infusion and hypersensitivity reactions can be severe and fatal. Most clinical trial and spontaneous cases of serious hypersensitivity occurred during or within the first hour after the completion of the infusion, although some cases report delayed acute onset (>4 hours but <4 days) or a delayed non-acute onset (4-21 days) hypersensitivity reactions.

Infections have been reported with administration of belimumab and are also associated with both SLE and immunosuppressant medication used to treat SLE. The mechanism of action of belimumab may increase the potential risk for the development of infections.

Table 1-3 provides a summary of key issues, their impact, and strategy to mitigate risk in this study.

Table 1-3 Summary of Key Issues, Their Impact and Strategy to Mitigate Risk

Identified Risks	Summary of Data	Impact – Eligibility Criteria	Strategy and Monitoring

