Post-infusion systemic reactions and Hypersensitivity	Administration of IV belimumab may result in infusion and hypersensitivity reactions, which can be severe and can be fatal. Non-serious infusion reactions and hypersensitivity reactions are common in SLE clinical trials with IV belimumab. Serious infusion and hypersensitivity reactions affected less than 1% of patients and included anaphylactic reaction, bradycardia, hypotension, angioedema, and dyspnea. Delays in the onset of hypersensitivity reactions have been observed. Infusion reactions following administration of belimumab occurred more frequently on the first 2 infusion days and tended to decrease with subsequent administrations. Delayed-type, non-acute hypersensitivity reactions have also been observed and included symptoms such as rash, nausea, fatigue, myalgia, headache, and facial oedema.	This identified risk does not directly impact eligibility criteria.	Subjects should remain under clinical supervision for 3 hours after completion of the first 2 infusions. Should symptoms of acute hypersensitivity occur, an extended period of monitoring may be appropriate, based on clinical judgment. Otherwise, subjects will be monitored during and after each infusion according to study sites' guidelines or standard operating procedure for IV infusions. This may include, but is not limited to, monitoring vital signs and observing for any untoward reactions. Subjects should be made aware of the potential risk, the signs and symptoms of such reactions, and the importance of immediately seeking medical attention. Belimumab should be administered by a healthcare professional prepared to treat hypersensitivity reactions including anaphylaxis.
Infections	Infections occurred in a slightly greater proportion of subjects treated with IV belimumab compared with placebo. Infections occurring in at least 3% of patients receiving belimumab and at least 1% more frequently than patients receiving	Exclude patients with any of the following: currently on any suppressive therapy for a chronic infection; hospitalization for treatment of an infection within 60 days of Day 0; use of IV or IM	Subjects should be made aware of the potential risk, the signs and symptoms of infection, and the importance of immediately seeking medical attention. Infections should be identified and treated appropriately.

Identified Risks	Summary of Data	Impact – Eligibility Criteria	Strategy and Monitoring

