8.5 Endpoints and Analysis

8.5.1 Safety Endpoint Definitions and Measurements

The table below describes the safety endpoints and measures collected in the study. All events shown in the table will be collected.

All-cause mortality
Serious Infections (including serious opportunistic infections and any event of TB or TB reactivation)
Non-serious opportunistic infections and other infections of interest (Appendix 2)
Malignancies (excluding NMSC)
Non-melanoma skin cancers
Psychiatric events suggesting serious mood disorders and anxiety
Suicidality (using C-SSRS; Appendix 4 and Appendix 5)
Serious Infusion and Hypersensitivity Reactions
All SAEs

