 - Serious Delayed Acute Hypersensitivity Reactions per GSK adjudication
 - Serious Delayed Non-Acute Hypersensitivity Reactions per GSK adjudication
- All Infections of Special Interest [see Section 9.5.12, protocol defined AESI]
 - Serious Infections of Special Interest
 - All opportunistic infections per GSK adjudication
 - Serious opportunistic infections per GSK adjudication
 - Opportunistic infections per GSK adjudication excluding Tuberculosis and Herpes Zoster
 - Serious opportunistic infections per GSK adjudication excluding Tuberculosis and Herpes Zoster
 - Active Tuberculosis
 - Non-Serious Active Tuberculosis
 - Serious Active Tuberculosis
 - Non-Opportunistic
 - Serious Non-Opportunistic
 - Opportunistic
 - Serious Opportunistic
 - Herpes Zoster
 - Serious Herpes Zoster
 - Non-Opportunistic
 - Serious Non-Opportunistic
 - Opportunistic
 - Serious Opportunistic
 - Recurrent

- Serious Recurrent
 - Disseminated
 - Serious Disseminated
- Sepsis
 - Serious Sepsis
- Depression/suicide/self-injury
 - Depression (Inc. mood disorders and anxiety)
 - Serious Depression (Inc. mood disorders and anxiety) [see Section 9.5.12, protocol defined AESI]
 -
 - Suicide/self-injury
 - Serious Suicide/self-injury
 - Serious Suicide/Self-injury per GSK Adjudication
 - Suicidal behavior per GSK Adjudication
 - Completed Suicide per GSK Adjudication
 - Suicidal Ideation per GSK Adjudication
 - Self-injurious Behavior Without Suicidal Intent per GSK Adjudication
- Deaths (using start date of fatal SAE to determine whether event occurred during the relevant study period)
- Deaths (using end date of fatal SAE i.e. date of death to determine whether event occurred during the relevant study period)

A listing of all PSAP-defined AESIs will be produced.

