- b. 2 AEs, 1 coding to a Category B preferred term and the other coding to a Category C preferred term *or*
- c. 2 AEs, 1 coding to a Category D preferred term and the other coding to either a Category B preferred term or to a Category C preferred term.

For the algorithmic search, if any event at a given infusion/injection meets the definition under criteria a, b or c, then all events in Categories A, B, C and D associated with that injection/infusion will be considered AESI.

GSK SRT will review all serious events identified via the broad search using a 21-day window from the start of an infusion/injection (see PSAP Section 8.3.2 for the definition of the assessment windows), and adjudicate these events as post-infusion/injection systemic reactions or hypersensitivity reactions per the criteria in [Section 16.2](#). Therefore, the window for the narrow, broad and algorithmic searches of AE and SAE data from the clinical database for SRT reporting (PSAP Section 13.3) is 21 days to correspond to the window for adjudication. Adverse events with partial or missing start dates will be included unless there is evidence through comparison of partial dates to suggest otherwise.

Note, for CSR reporting, narrow, broad, and algorithmic searches of AE and SAE data will be run using a 3-day window from the start of an infusion/injection.

Sampson Criteria

Sampson et al define anaphylaxis as a severe, potentially fatal, systemic allergic reaction that occurs suddenly after contact with an allergy-causing substance. In addition, one of the following 3 criteria must be met: (1) acute onset of illness with involvement of skin or mucosal tissue, accompanied with either respiratory compromise, reduced blood pressure, or hypotension-related symptoms of end-organ dysfunction (2) reduced blood pressure associated with a known allergen or (3) two or more of the following that occur rapidly after exposure to an allergen: a) involvement of skin-mucosal tissue b) respiratory compromise c) reduced blood pressure d) persistent GI symptoms.

With the exception of GI symptoms, all symptoms required to assess anaphylaxis per Sampson criteria would be identified by Broad Anaphylaxis SMQ or the Anaphylactic Reaction SMQ algorithmic. Therefore, any events falling under the below criteria will be adjudicated by SRT prior to database release to determine if serious anaphylaxis per Sampson criteria is met.

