Tumors of unspecified malignancy, as identified per the terms in [Section 17.1](#), will be reviewed clinically by the GSK SRT for reporting. In general, non-serious events in the tumours of unspecified malignancy with insufficient information will be categorized as not malignant. Serious adverse events with insufficient information will be categorized as either not malignant or malignant based on the type of tumor and likelihood the tumor type is malignant (e.g., thyroid nodules are common in SLE patients and are generally not malignant; tumor types with higher likelihood for malignancy would be assumed to be malignant).

Section 16.2: Serious hypersensitivity and post-infusion/injection systemic reactions

GSK SRT will review all serious cases identified from the Broad Anaphylaxis SMQ as described in [Section 15](#) and [Section 17.1](#), applying clinical judgment to determine if the preferred terms are indicative of a hypersensitivity or post-infusion/injection reaction. Time to onset after an infusion/injection and details provided in the clinical narratives with respect to the nature and likely cause of the events are taken into consideration. The GSK SRT adjudicates serious hypersensitivity reactions into a category based primarily on time to onset: acute (onset < 24 hours), delayed acute (onset 2-3 days), or delayed, non-acute (onset 4-21 days). In addition to time to onset, description of associated symptoms is taken into account for this categorization. In studies where subjects are

receiving weekly injections, any delayed, non-acute reactions will typically occur in the interval 4-7 days later, but may occur up to 21 days later following a missed injection or after the last injection.

In addition, possible cases of serious anaphylaxis per Sampson criteria will be identified per the criteria in [Section 15](#). Any events falling under these criteria will be adjudicated by GSK prior to database release to determine if serious anaphylaxis per Sampson criteria is met.

Section 16.3: Potential opportunistic infections

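### The estimate for serious infusion and hypersensitivity reactions stops 3 days after an infusion, so nearly all delayed non-acute (Day 4-21) reactions get counts but no between-arm difference or CI

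*SAP*

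**What the plan says.** Protocol Section 8.5.1 names the endpoint "Serious Infusion and Hypersensitivity Reactions" and sets no onset window. Protocol Section 1.4.1 says that, although most serious cases occur close to the infusion, some show "a delayed non-acute onset (4-21 days) hypersensitivity reactions". Table 1-3, in the row for this same identified risk, adds that "Delayed-type, non-acute hypersensitivity reactions have also been observed".

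Week 52 RAP Section 9.5.12 turns the endpoint into all SAEs from the broad anaphylactic-reaction search, restricted by a window that "includes events on the day of the infusion or within 3 days after the infusion". The programming rule requires both the seriousness flag (AESER) and the 3-day infusion flag (AEINF3FL). Section 11.2.4 marks this 3-day serious broad-search row as the protocol-defined AESI.

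The window comes from the programme safety plan reproduced in Appendix 6: "for CSR reporting, narrow, broad, and algorithmic searches of AE and SAE data will be run using a 3-day window". The same appendix has the sponsor's safety review team (SRT) review all serious broad-search events over 21 days. The SRT classes hypersensitivity reactions as acute, delayed acute (2-3 days) or delayed non-acute (4-21 days). Section 11.2.4 gives the last class its own line, "Serious Delayed Non-Acute Hypersensitivity Reactions per GSK adjudication".

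Section 11.1.2 specifies the difference in percentages with 95% CI for protocol-defined AESIs. For the categories in Section 11.2.4 it is only the number and percentage of subjects and the number of events.

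**The concern.** Protocol Section 8.1 gives the study's main purpose as the between-arm difference, with a 2-sided 95% CI, for each prespecified AESI and for mortality. Protocol Section 1.3 names serious infusion and hypersensitivity reactions among the areas where earlier controlled trials showed a numerical imbalance. For this AESI, the planned interval covers two of the sponsor's three onset classes and leaves out nearly all of the third.

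RAP Section 2.2.1 says that Section 2.2.3 explains where AESI definitions depart from the protocol. Section 2.2.3 does so for serious infections, where it drops non-serious tuberculosis. It says nothing about the 3-day limit. A reader of Tables 2.05 and 2.06 or the dot plots could therefore take the interval as covering the risk as the protocol describes it.

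**Working it through.** The plan states no rate, sample size or precision for this endpoint, so there is no figure of its own to reproduce. The planned interval method (simple asymptotic, RAP Section 11.1.1) can be checked on mortality with half-width = 1.96 × √(2p(1−p)/n):

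- p = 0.68%, n = 2,500 per arm: 0.456%.
- p = 0.564%, n = 2,000 per arm: 0.464%.

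Both round to the stated ±0.46%, so the formula is the one in use.

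**Window count**

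- Infusions fall on Days 0, 14 and 28, then every 28 days to Week 48 (protocol Section 5.3): 14 infusions.
- On-treatment days run from Day 0 to Day 336 + 28 = 364, so 365 days.
- Days 0-3 after an infusion: 14 × 4 = 56 days (15% of 365).
- Days 4-21 after an infusion: 14 × 18 = 252 infusion-by-day slots.
- Overlap: Days 14-17 after infusions 1 and 2 are Days 0-3 of the next infusion, so 2 × 4 = 8 slots are still flagged. From Day 28 the 28-day gap leaves no overlap.
- Outside the flag: 252 − 8 = 244 (97%).

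These are calendar slots, not events. They show what the rule covers, not how many reactions it misses.

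**Events affected**

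Protocol Section 1.2 gives 31/5,366 belimumab subjects (0.58%), or 0.28 per 100 subject-years, pooled over all SLE studies.

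- By proportion: 31/5,366 × 2,000 = 11.6.
- By rate, one year each: 0.28/100 × 2,000 = 5.6.
- The two differ because 31/0.0028 ≈ 11,070 subject-years, about 2.1 years per subject.
- Assumed delayed non-acute share of 10-30%: 0.10 × 5.6 ≈ 0.6 up to 0.30 × 11.6 ≈ 3.5 events in the belimumab arm.

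The share is an assumption that nothing in the documents anchors, and they give no placebo rate for serious reactions.

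**Effect on the interval (assumed rates, 2,000 per arm)**

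The added column is belimumab subjects whose only event falls at Days 4-21. Four subjects is just above the 3.5 derived here.

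| Rate within 3 days, belimumab / placebo | Added | Difference (95% CI), % |
|---|---|---|
| 0.58% / 0.58% | 0 | 0.00 (−0.47 to 0.47) |
| 0.58% / 0.58% | 0.1% (2 subjects) | 0.10 (−0.39 to 0.59) |
| 0.58% / 0.58% | 0.2% (4 subjects) | 0.20 (−0.31 to 0.71) |
| 0.58% / 0.29% | 0 | 0.29 (−0.12 to 0.70) |
| 0.58% / 0.29% | 0.1% (2 subjects) | 0.39 (−0.04 to 0.82) |
| 0.58% / 0.29% | 0.2% (4 subjects) | 0.49 (0.04 to 0.94) |

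For an endpoint this rare, a few events move the estimate visibly. The table illustrates sensitivity and predicts nothing.

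**The case against.** The case for leaving the plan alone has real substance.

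- **The events are reported.** Delayed non-acute reactions have their own adjudicated line by arm in Section 11.2.4 and a summary over the first six infusions in Section 11.2.4.1. The PSAP-defined AESI table (3.037) is a headline result in Section 16.3. A reader might infer that a delayed signal would go unseen, and the documents do not support that. The missing item is a difference and interval, which can be computed from n and N.
- **The window is stated openly.** It is a programme convention, and Section 11 wants the detailed AESI summaries comparable across studies. The protocol supplies only a label, so the RAP had to define the endpoint. The study calendar marks this assessment at infusion visits only. This shows that the window is not a slip. It does not explain why the departure is absent from 2.2.3, or why the fuller onset range gets no interval.
- **A programmed search is reproducible.** Adjudication uses clinical judgment, including the likely cause. No section says that the SRT works blind, and protocol Section 6.7 allows sponsor safety staff to unblind any subject with an SAE. A reader might infer that the adjudicated set is the right endpoint and should replace the search. That is a debatable trade-off and the documents do not settle it. Replacement would also now be a redefinition after unblinding.
- **Few delayed events may exist.** Protocol Section 1.2 says that most serious cases occurred during the infusion or within an hour after it. This stands, and it is why the size remains an assumption.

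**Conclusion.** The point holds in a limited form and is a cheap improvement. The between-arm difference and 95% CI for this AESI omit nearly all serious reactions at Days 4-21 (97% of slots on the nominal schedule), although the protocol endpoint has no time limit and the protocol includes those reactions in the risk. The restriction is missing from the list of departures.

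Two stronger statements should be avoided. A reader might infer that every delayed reaction is excluded, but the early 14-day intervals leave 8 of 252 slots inside the next infusion's window, and visit windows could add a few more. A reader might also infer a loss of several events in each arm, but the source figure is for belimumab only. Under the assumed 10-30% share, the range is about 0.6 to 3.5 events in the belimumab arm, and nothing can be said for placebo.

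The conclusion also depends on the RAP Addendum of 13-DEC-2018 and the mock shells, neither of which was supplied. Either may already provide the interval.

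**What to change.** 1. Keep the 3-day broad search in Section 9.5.12 as the programmed row.
2. Add one row beside it in Tables 2.05 and 2.06 and in the dot plots: serious reactions that the SRT adjudicates as acute, delayed acute or delayed non-acute within 21 days of an infusion, with n, %, difference and 95% CI by the method already planned.
3. List the 3-day restriction and its reason in Section 2.2.3.
4. First check whether the December 2018 Addendum already does this. The Years 2 to 5 RAP dates the Week 52 unblinding to 2-JAN-2019, so a row added after that should be labelled supplementary, with the 3-day result left unchanged.

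The cost is one row and one sentence. No new data are needed, because Section 9.2 already requires the adjudications to be confirmed before database freeze. The downside is that the added row rests on sponsor adjudication. A footnote should say so and state whether the adjudicators were blind to treatment.
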